11.2.1.5 Additional Data of Interest

Additional information will be collected to characterize the study population, implanted system, and progress of the clinical investigation. The data will be statistically analyzed, where appropriate. Further data of interest will include:

- Patient Global Assessment (PGA) at each visit
- MPP programmed settings
- Adverse events attributed to MPP feature
- Device initial and final programmed settings
- Methods utilized to optimize MPP, AV and/or V-V timing

11.2.2 **Study Size and Duration**

The MPP sub-study will enroll up to 100 subjects at up to 75 sites within the United States who are participating in the QP ExCELS study. Subjects in the MPP sub-study will be followed for 6 months (180 ± 30 days post-MPP enrollment). Subjects enrolled in the MPP sub-study will rejoin the main QP ExCELS study after completion of their 12-month MPP follow-up[§].

11.2.3 **Sample-Size Analysis**

The investigation is designed to limit the number of patients involved while still exposing the device to a sufficiently large patient population in order to ensure a representative and statistically meaningful sample.

Primary Endpoint 1 Sample Size

The estimated sample size requirements are based on a superiority comparison of the proportion of responders to a performance goal of 3%, chosen based on the assumption that any conversion of non-responders to responders is clinically relevant. A performance goal of 3% was chosen rather than 0% to account for variability (“noise”) around 0%, for example, due to infrequent subjects who are late responders to CRT or improve regardless of MPP. The expected result is estimated at a 10% conversion of non-responders to responders.

There is limited published data available for mid- to long-term follow-up CRT response with multiple point LV pacing in any population. Additionally, no published data could be found related to CRT response with multiple point LV pacing in an “all-comer non-responder” population. The St. Jude Medical MultiPoint Pacing IDE Study^{3,5} (“St. Jude IDE study”, NCT01786993) evaluated CRT response based on a Clinical Composite Score (CCS) after 3 months of BiV pacing. Subjects were then randomized to the MultiPoint™ Pacing treatment arm

[§] If an MPP sub-study subject was enrolled at the 3-Month QP ExCELS follow-up, they will re-join the main QP ExCELS study after completion of their 9-month MPP follow-up.

or to continue on with BiV pacing. The study showed that 70.1% of subjects were responders to MultiPoint™ Pacing. However, both responders and non-responders after 3 months of BiV pacing were included in the MultiPoint™ Pacing treatment arm. Additionally, the St. Jude IDE study only randomized subjects with acute "equal or better" EA velocity time integral (VTI) with MultiPoint™ Pacing vs. BiV pacing per echocardiogram at the 3-Month Visit. There were 52 subjects that did not meet this criterion and were not randomized. Thus, subjects that may likely have not responded to multiple point LV pacing therapy were not randomized which certainly led to a higher response rate to MultiPoint™ Pacing.

BIOTRONIK proposes to allow enrollment of any QP ExCELS subject meeting non-responder criteria ("all-comer non-responders") at the 6-Month Follow-up into the MPP sub-study as it is not standard of care to perform echocardiograms on CRT subjects to determine if they are responding to standard CRT therapy. As such, we estimate that the proportion of non-responders at 6-months that will be converted to responders at 12-months will be less than that observed in the St. Jude IDE study. There are three additional studies which have published results for CRT response with MPP measured via CCS or NYHA improvement with mid- to long-term follow-up (6 to 12 months)^{2,6,7}. However, these studies also did not limit multiple point LV pacing treatment to non-responders, and thus the results are not directly applicable to the proposed BIOTRONIK study design.

Assumptions:

- Study Design: Superiority Trial
- Type I error (alpha): 0.025 (one-sided)
- Statistical power: 80%
- Performance Goal: 3%
- Expected: 10%

A total of 90 evaluable subjects would be required to demonstrate superiority to a performance goal of 3%.

11.2.4 Data Analyses

Classification of "HF hospitalization" and "cardiovascular death" events for use in primary endpoint 1, secondary endpoint 2, and secondary endpoint 3 analyses will be determined by a Clinical Events Committee (Section 11.3.4).

Descriptive statistics will be used to present and summarize the data collected in the clinical study. Frequency distributions and cross tabulations will be presented for discrete variables. Means, standard errors, and ranges will be presented for continuous variables.

For primary endpoint 1, the lower, one-sided, exact 97.5% bound for the observed proportion of responders ("improved") would have to exceed 3% for rejection of the null hypothesis.

Additional related analyses to be performed for the endpoint include:

- Descriptive statistics for observed changes in NYHA class and frequency tabulations for the other components of the Clinical Composite Score.

11.2.4.1 Adjustments to Overall Study Sample Size

Assuming a 10% loss to follow-up rate during the study for reasons unrelated to the study outcomes, a total enrollment of 100 subjects (90/0.9) would be required to achieve an evaluable study population of 90 subjects.

11.2.4.2 Replacement of Missing Data

The last observation carried forward (LOCF) principle will be utilized for the analysis of NYHA Classification and Patient Global Assessment for primary endpoint 1 and secondary endpoints 2 and 3.

Missing NYHA and patient global assessment data at either the enrollment or follow-up visits affects the number of subjects that can be included in the analysis. It is possible that subjects or investigational personnel may either forget or choose not to answer one or more of the questions related to NYHA classification or patient global assessment.

11.2.4.3 MPP Programming

Subjects are expected to remain programmed with the MPP feature ON from MPP enrollment through the completion of the sub-study. Subjects who have the MPP feature permanently turned OFF prior to completion of the sub-study will be required to report a protocol violation. Subjects with MPP permanently turned OFF prior to completion of the sub-study will be analyzed as intent to treat.

Subjects may have the MPP feature temporally turned OFF due to a lead revision procedure and these short durations with MPP will not be reported as a protocol violation or analyzed differently. Additionally, any QP ExCELS subject that does not enroll into the MPP sub-study but receives MPP due to the physician's determination will not be analyzed towards the MPP study endpoints.

11.3 Protocol Requirements

11.3.1 Patient Population

The investigator is responsible for screening all potential patients and selecting those who are appropriate for study inclusion. The patients selected for participation should be from the investigator's general patient population currently participating in the QP ExCELS study according to the inclusion and exclusion criteria described below.

11.3.1.1 Inclusion Criteria

To support the objectives of this investigation, the inclusion criteria at the time of patient enrollment for this investigational study include the following requirements:

- Currently enrolled in the ongoing QP ExCELS study
- Successfully implanted with a BIOTRONIK Ilivia 7 HF-T QP family CRT-D system, or future-marketed CRT-D system with the MPP feature. Successful implantation is defined as having at least two LV pacing vectors with a measured pacing threshold of ≤ 5.0 V @ any pulse width (allowing for a minimum 2.5 V safety margin) without phrenic nerve stimulation at the final programmed pacing output at the time of enrollment into the MPP sub-study.
- CRT Responder Assessment classification as “Worsened” or “Unchanged”
- Standard continuous biventricular (BiV) pacing from implant until the 6-Month QP ExCELS follow-up visit. (Implant to 3-Month QP ExCELS follow-up who qualify due to a HF hospitalization event)
- Able to understand the nature of the sub-study and give informed consent
- Available for an additional follow-up visit specific to the MPP sub-study at the investigational site
- No evidence of non-compliance to their ongoing commitment in the QP ExCELS study

11.3.1.2 Exclusion Criteria

To support the objectives of this investigation, the exclusion criteria at the time of patient enrollment include the following requirements:

- Have a life expectancy of less than 6 months
- Expected to receive heart transplantation or ventricular assist device within 6 months
- Chronic atrial fibrillation
- Presence of another life-threatening, underlying illness separate from their cardiac disorder
- Received MPP pacing prior to enrolment into the MPP sub-study

11.3.2 **Specific Testing**

This sub-study protocol involves very specific inclusion and exclusion criteria. Therefore, detailed evaluation of all patients before enrollment is important to the success of the trial.

The specific visits that are part of the study are provided below. Specific Procedures are described in more detail in the following sections.

- MPP Enrollment (QP ExCELS 6-Month follow-up or 3-Month follow-up with HF hospitalization)
- 9-Month MPP Follow-up
- 12-Month MPP Follow-up

Subjects enrolled in the QP ExCELS MPP sub-study will be evaluated at the MPP enrollment visit, then 3- and 6-months post MPP enrollment. Subjects enrolled in the MPP sub-study will rejoin the main QP ExCELS study after the 12-Month** Follow-up; however, no further specific MPP related data will be assessed. Subjects with a HF Hospitalization event, as classified by investigator, prior to 90 days post implant may be enrolled into the MPP sub-study at the 3-Month follow-up visit.

11.3.2.1 New York Heart Association (NYHA) Classification

During the course of the study, the NYHA classification will be utilized for evaluation of the specific level of cardiac disease. The NYHA class will be evaluated and reported by the study investigator. The NYHA will be evaluated at all protocol-defined follow-ups. The following bullets provide the definitions for each class:

- Class I: Subjects with cardiac disease, but without resulting limitation of physical activity. Ordinary physical activity does not cause undue fatigue, palpitation, dyspnea, or anginal pain.
- Class II: Subjects with cardiac disease resulting in slight limitation of physical activity. They are comfortable at rest. Ordinary physical activity results in fatigue, palpitation, dyspnea, or anginal pain.
- Class III: Subjects with cardiac disease resulting in marked limitation of physical activity. They are comfortable at rest. Less than ordinary activity causes fatigue, palpitation, dyspnea, or anginal pain.
- Class IV: Subjects with cardiac disease resulting in inability to carry on any physical activity without discomfort. Symptoms of cardiac insufficiency or of anginal syndrome may be present even at rest. If any physical activity is undertaken, discomfort is increased.

The description for each of the classes was taken from the ACC/AHA Guidelines for Implantation of Cardiac Pacemakers and Antiarrhythmia Devices⁸.

11.3.2.2 Patient Global Assessment (PGA)

[figure not shown]
During the course of the study a patient global assessment will be given to assess how the subject's overall status has changed since prior to receiving CRT therapy (markedly better, better, unchanged, worse, markedly worse). It is important to minimize the influence on the respondent by limiting their interaction and verbal exchanges with spouses or other individuals who may affect results while the assessment form is being completed.

** Subjects enrolled in the MPP sub-study at the 3-Month QP ExCELS follow-up, qualifying with a HF hospitalization event, will rejoin the main QP ExCELS study after the 9-Month Follow-up

11.3.3 Sub-Study Procedures

Figure 13 provides an overview of the MPP sub-study design as part of the QP ExCELS study. Details of subject eligibility requirements and specific study procedures are noted in Section 11.3.1. While participating in the MPP sub-study, all subjects will continue to complete all required QP ExCELS study follow-ups.

Figure 14: MPP Sub-Study Design

* 3 Month follow-up if heart failure hospitalization event occurred.

A subject may qualify as a CRT non-responder and be enrolled at the 3-month follow-up if a HF hospitalization has occurred while receiving standard bi-ventricular pacing.

11.3.3.1 Enrollment into MultiPole Pacing Sub-Study

Prior to enrollment, the patient's background and history must be reviewed in order to ensure that the patient is an appropriate candidate for this sub-study. In addition, as part of the clinical study, informed consent must be obtained from the patient prior to initiating any study-related procedures.

Subjects enrolled in the QP ExCELS study evaluation who reach the 6-month post-implant follow-up with a CRT Responder Assessment as Unchanged or Worsened and meet the sub-study inclusion/exclusion may be enrolled into the sub-study. Subjects at the 3-month QP ExCELS follow-up with a HF hospitalization event since the QP ExCELS implant will be considered worsened and may be enrolled at the 3-month visit. Subjects are considered enrolled in the sub-study once MPP sub-study informed consent is obtained.

MPP optimization may be performed or not performed per investigator discretion at the time of enrollment into the MPP sub-study. The investigator will determine if MPP optimization will be performed for each subject and which method will be used (e.g. QRS width, electrical delay, echocardiography, etc.). MPP programmed parameters may be adjusted as needed during the follow-up period for MPP sub-study subjects.

The following data will be collected at the MPP enrollment visit:

1. Collect all lead testing data for standard QP ExCELS study follow-up
2. Turn MPP ON and collect MPP programmed settings
3. Document MPP optimization method
4. Obtain NYHA classification and HF hospitalization status
5. Obtain Patient Global Assessment
6. Collect device initial and final programmed settings
7. Document any reportable Adverse Events
8. Review and complete the appropriate eCRFs

The MPP feature must be programmed ON from MPP enrollment until the subject exits the sub-study. Subjects who have the MPP feature permanently turned OFF prior to completion of the sub-study will be required to report a protocol violation.

MPP follow-up windows are ± 30 days. Care should be given to ensure scheduling of MPP study visits fall within the corresponding QP ExCELS visit windows (± 45 days).

11.3.3.2 9-Month MPP Follow-up^{††}

At a 9-month follow-up (90 ± 30 days post-MPP enrollment), subjects return to the investigational site for an in-office assessment of their heart failure status and implanted system.

The following data should be collected:

1. Collect MPP programmed settings
2. Obtain NYHA classification and HF hospitalization status
3. Obtain Patient Global Assessment
4. Collect device initial and final programmed settings
5. Document any reportable Adverse Events
6. Review and complete the appropriate eCRFs

11.3.3.3 12-Month MPP Follow-up^{‡‡}

At the QP ExCELS 12-month follow-up (180 ± 30 days post-MPP enrollment), subjects return to the investigational site for an in-office assessment of their heart failure status and implanted system.

1. Collect all lead testing data for standard QP ExCELS study follow-up
2. Collect MPP programmed settings
3. Obtain NYHA classification and HF hospitalization status
4. Obtain Patient Global Assessment
5. Collect device initial and final programmed settings
6. Document any reportable Adverse Events
7. Review and complete the appropriate eCRFs

Following the 12-month follow-up, all subjects may be programmed to MPP or standard BiV pacing, per physician discretion.

11.3.4 Clinical Events Committee – MPP Sub-Study Events

The QP ExCELS Clinical Events Committee (CEC) described in Section 5.1 will adjudicate all adverse events that require additional invasive intervention to resolve which may be related to the MPP feature. These events include any software issues related to MPP programming or any adverse event that occurs while MPP is enabled and that may be attributed to the use of the MPP feature. The CEC will

^{††} Subjects enrolled at the 3-Month follow-up due to a prior HF hospitalization event will be followed at 6-months (90 ± 30 days post-MPP enrollment).

^{‡‡} Subjects enrolled at the 3-Month follow-up due to a prior HF hospitalization event will be seen at 9-months (180 ± 30 days post-MPP enrollment) and join the main QP ExCELS study at the 12-Month visit.

indicate whether the adverse event is related, possibly related, not related, or has an unknown relation to the MPP feature.

In addition, the CEC will adjudicate all deaths reported while participating in the MPP sub-study and classify each death as cardiovascular, vascular, non-cardiovascular/vascular, or unknown.

The CEC will adjudicate all reported protocol-defined hospitalizations while a subject is enrolled in the MPP sub-study. Hospitalization events will be classified as cardiovascular, vascular, non-cardiovascular/vascular, or unknown. Additionally, hospitalizations classified as cardiovascular will be further classified as a HF hospitalization, non-HF hospitalization, or unknown. Hospitalization events reported by the investigator as part of the initial responder classification for enrollment into the MPP sub-study will not be adjudicated by the CEC.

11.4 Benefits and Risks

11.4.1 Potential Benefits

The clinical benefit of the Ilivia HF-T CRT-D is similar to that of standard CRT-Ds. Subjects taking part in this sub-study will receive additional and detailed examinations of their CRT system.

Although the participating study subjects might benefit from the new CRT-D system with MPP feature, currently there is only limited benefit for enrolled study subjects. Studies have shown that multiple point LV pacing via a QP LV lead may be an alternative approach to improve CRT response by delivering multiple LV pacing pulses, simultaneously recruiting a larger volume of myocardium.² A recent IDE study showed that quadripolar multiple point LV pacing was non-inferior to standard quadripolar biventricular pacing.³ The medical community, as well as future subjects, may benefit from these study results, which will enable a better understanding of the safety and efficacy of the MPP feature.

11.4.2 Potential Risks

During the course of this sub-study subjects may experience potential adverse events related to the MPP feature. Although not expected these risks may include excessive battery drain or phrenic nerve stimulation. There is no current data to support superiority of MPP to conventional BiV pacing and it is not known if this feature will turn a non-responder into a responder. Adverse events will be determined by the investigator during subject follow-ups, documented in the subject medical record, and reported in the EDC system. Documentation includes the evaluation of the relation between the adverse event and the MPP feature. The date of the adverse event and resolution must be recorded. When an adverse event is noted in the EDC system, corrective action will also be provided with any supportive documentation available. Corrective actions may include, for example: drug therapy changes, programming changes, lead repositioning, new lead implants, or CRT-D explant.

Study sites may report adverse events through MedWatch, FDA's adverse event reporting tool for market-released devices. As defined in BIOTRONIK's internal procedures, these adverse events may be reported by BIOTRONIK through manufacturer's MedWatch reports.

11.5 Other General Information

11.5.1 Subject Death

Personnel at the investigational site should notify BIOTRONIK as soon as possible concerning any subject death during the investigation. This notification should include a completed study termination eCRF, death certificate, and a copy of the notification of the death sent to the IRB. If a death certificate is not available, a detailed statement (death report) signed by the investigator should be written in addition to the termination eCRF. The death report should include all of the following, if available:

- date and time of death
- place death occurred
- identification of the rhythm at the time of death, if known (include any available documentation)
- immediate cause of death
- any other circumstances surrounding the death
- whether it was device or procedure related

All implanted devices that are involved with the investigational study should be removed and returned to BIOTRONIK.

All deaths occurring while enrolled in the MPP study will be reviewed by the CEC.

11.5.2 Reporting Hospitalizations

To eliminate possible bias at the site level related to possible endpoint events of the MPP sub-study, adverse events requiring hospitalization for any cardiovascular hospitalizations and any other hospitalizations in which cardiovascular symptoms occur will be collected while subjects are enrolled in the MPP sub-study. Each hospitalization will be adjudicated to determine whether it meets the MPP sub-study endpoint criteria as a heart failure hospitalization by the Clinical Events Committee (CEC).

BIOTRONIK will be responsible for verifying completeness of the initial reported event and coordinating with sites to obtain any missing or additional source documentation required by the CEC to adjudicate the case. Additional documentation will be requested from the enrolling site as needed. The hospital report should include the following, if available:

- Discharge summary
- History and physical and admission summary.
- Diagnostic and laboratory test results.
- Chest X-ray, echocardiography, ultrasound or other imaging test results, as appropriate.
- Consultations, operation reports, progress notes and discharge summaries from the subject medical records.
- Investigator description and assessment of the event.

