11.5.3 Definition of Heart Failure Hospitalization

Hospitalization for worsening heart failure is defined as a hospitalization that includes increased signs and/or symptoms of worsening heart failure requiring the administration or augmentation of intravenous or oral heart failure therapy (e.g., inotropes, diuretics, and/or vasodilators).

A hospitalization classification will be based on the primary admission diagnosis, not on the development of new events that occur during the hospitalization.

For each hospital admission, the investigator will be requested to state whether or not the subject experienced worsening heart failure at the time of admission or during the admission, and if so, whether or not this was the primary reason for admission or secondary to an obvious precipitating factor such as atrial fibrillation. The investigator will also be asked to state whether or not the subject received an intravenous medication for heart failure including diuretics, vasodilators or inotropic agents or a substantial increase in oral diuretic therapy for heart failure.

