11.5.4 Adverse Events

In addition to the adverse events reportable for the main QP ExCELS study, Section 6.2, the investigator shall report to the sponsor by completing the appropriate eCRF, the following type of events specific to the MPP sub-study:

- Any cardiovascular hospitalizations and any other hospitalizations in which cardiovascular symptoms occur on or before the date of the 12-Month follow-up^{§§}.
- All adverse events that required additional invasive intervention to resolve, specifically related to the MPP feature of the CRT-D. These adverse events include any software issues related to MPP programming for any adverse event that occurs while MPP is enabled and that may be attributed to the use of the MPP feature.

^{§§} 9-month follow-up for subjects enrolled at the 3-month follow-up.

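### In the MPP sub-study the site decides which hospital admissions reach the Clinical Events Committee, leaving a small under-reporting risk that can only favour MPP

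*Combined protocol and SAP*

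**What the plan says.** Section 11.5.2 opens with its aim: "To eliminate possible bias at the site level related to possible endpoint events of the MPP sub-study". The rule that follows has two parts. The site reports cardiovascular hospitalizations, and in addition "any other hospitalizations in which cardiovascular symptoms occur will be collected while subjects are enrolled in the MPP sub-study". Section 11.5.4 repeats the rule and adds the end date: "Any cardiovascular hospitalizations and any other hospitalizations in which cardiovascular symptoms occur on or before the date of the 12-Month follow-up" (the 9-month visit for subjects who entered at 3 months). The MPP bullet in Section 6.2 says the same.

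Section 11.3.4 has the Clinical Events Committee (CEC) adjudicate the protocol-defined hospitalizations that are reported. "Hospitalization events will be classified as cardiovascular, vascular, non-cardiovascular/vascular, or unknown", and those found cardiovascular are then split into heart failure, non-heart-failure or unknown. Under 11.5.2 the sponsor checks that an event already reported is complete.

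Section 11.5.3 defines a heart failure hospitalization by increased signs or symptoms of worsening heart failure that need heart failure therapy, and bases the class on the primary admission diagnosis. It also says: "For each hospital admission, the investigator will be requested to state whether or not the subject experienced worsening heart failure".

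Under 11.2.1.1 a subject is Improved only with no heart failure hospitalization, no cardiovascular death and a better NYHA class. The investigator rates NYHA (11.3.2.1). The sub-study is single-arm, with MPP programmed on at enrollment (11.2, 11.3.3.1).

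**The concern.** Central adjudication protects against site bias only for the cases that reach the committee. Here the site screens first. It must decide whether an admission is cardiovascular and, if not, whether cardiovascular symptoms occurred. The plan does not define cardiovascular symptoms. Breathlessness or oedema in a patient with lung or kidney disease is where that judgement is hardest, and it is the kind of case a committee exists to settle.

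The investigator who applies the screen knows that MPP is on and also rates NYHA class. One person therefore influences both the gain that makes a subject Improved and the first look at the event that would cancel it.

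The error runs one way. An unreported heart failure admission can keep a subject out of Worsened but cannot put one there. It bears on primary endpoint 1 and on secondary endpoints 2 and 3. On secondary endpoint 3 an unchanged NYHA class is enough to count as a responder, so a missed admission matters there even without a NYHA gain. There is no control arm in which the same error would offset it.

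**Working it through.** **1. Who sees what.**

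| Step | Section | Who decides | Scope |
|---|---|---|---|
| Report the admission | 6.2, 11.5.2, 11.5.4 | Site | Cardiovascular, or other with cardiovascular symptoms |
| Check completeness | 11.5.2 | Sponsor | Events already reported |
| Classify | 11.3.4 | CEC | Reported, protocol-defined hospitalizations |
| Heart failure status at MPP visits | 11.3.3.2, 11.3.3.3 | Site | The site's own answer |
| Deaths | 11.3.4, 11.5.1 | CEC | All deaths during the sub-study |

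Deaths reach the committee whatever their cause; admissions do not. No section requires a list of all admissions or an independent search for unreported ones.

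**2. The plan's own sample size.** Inputs from 11.2.3 and 11.2.4: performance goal 3%, expected rate 10%, one-sided alpha 0.025, power 80%, exact lower 97.5% bound above 3%. For n = 90:

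- The smallest r with P(X ≥ r | 90, 0.03) ≤ 0.025 is r = 7, with actual alpha 0.0188.
- Power = P(X ≥ 7 | 90, 0.10) = 0.8075. With n = 89 it is 0.798.
- 90/0.9 = 100 enrolled.

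The stated 90 and 100 reproduce. Collecting more admissions changes none of these figures.

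**3. How many false Improved scores reverse the result.** Exact (Clopper-Pearson) lower bounds:

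| Improved | Lower bound | Result |
|---|---|---|
| 6/90 | 2.49% | fails |
| 7/90 | 3.18% | passes |
| 8/90 | 3.92% | passes |
| 9/90 | 4.68% | passes |

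One false Improved (7 − 1 = 6) reverses the result only if exactly 7 are observed. At the expected 9/90 it takes 9 − 6 = 3.

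**4. Effect on the error rate.** Suppose the true rate equals the 3% goal and false Improved scores add d to it. Then P(X ≥ 7 | 90, 0.03 + d) is:

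| d, percentage points | Chance of passing |
|---|---|
| 0 | 1.88% |
| 0.1 | 2.20% |
| 0.5 | 3.87% |
| 1.0 | 6.92% |

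The nominal 2.5% is reached at d = 3.18 − 3.00 = 0.18 points, or about 0.0018 × 90 = 0.16 subjects on average. These rows show sensitivity and do not estimate d.

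**5. Why d cannot be estimated.** It is a product of four rates: h (heart failure admission within six months) × m (site calls it non-cardiovascular) × u (site also judges that no cardiovascular symptoms occurred, or does not report) × i (NYHA class nevertheless better). The documents give none of them. As pure assumption, take h = 0.15, m = 0.175, i = 0.15, so h × m × i = 0.39 points:

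| u | d, points | Chance of passing |
|---|---|---|
| 1 | 0.39 | 3.4% |
| 0.5 | 0.20 | 2.55% |
| 0.25 | 0.10 | 2.2% |

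With wider assumptions (h 0.10–0.20, m 0.10–0.25, i 0.10–0.20) and u = 1, d runs from 0.1 to 1.0 points and the chance of passing from 2.2% to 6.9%. Setting u = 1 means the symptom part of the rule never works, so these are upper figures for the inputs chosen.

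**The case against.** The strongest defence is the second part of the rule. It turns on symptoms, not on the cause the site assigns. A heart failure hospitalization by definition involves heart failure signs or symptoms, so an admission blamed on the lungs or kidneys is ordinarily still reportable. A reader might infer that misattribution alone keeps such an admission from the committee. The text does not support that: the site must also judge the symptoms non-cardiovascular, or fail to report. This part of the defence stands and narrows the gap, but the second judgement is still the site's.

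A reader might also see a contradiction between 11.5.3 and 11.5.2. The phrase about each admission follows directly after the reporting section and can mean each reported admission. It is an ambiguity. Nor does the committee's non-cardiovascular class in 11.3.4 show that all admissions were meant to be sent: the symptom part already sends it such cases.

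Other safeguards exist. Heart failure status is asked again at the MPP visits, the sponsor pursues missing documents, and there is on-site and centralized monitoring (9.1). They lower the risk. But the same site answers the visit question, the document check begins with a reported event, and the monitoring section names no search for unreported admissions.

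Finally, classification follows the primary admission diagnosis, so some extra admissions would be classed non-heart-failure anyway, and a subject is falsely Improved on the primary endpoint only if NYHA class also improved. Both points stand and limit the size.

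**Conclusion.** The point holds as a residual risk of under-ascertainment. In an open, single-arm sub-study the site makes the first decision, the committee sees only reported admissions, and nothing specified would find the rest. The direction is certain: any such miss favours MPP. The size is not known. One false Improved decides the result only at exactly 7/90, and at the expected 9/90 three would be needed. The error rates in the working rest on assumed values.

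The documents do not support saying that the protection against site bias in 11.5.2 fails, or that the false-positive rate reaches any particular figure. The rule should capture most misattributed heart failure admissions. It leaves one avoidable judgement with the party whose bias 11.5.2 sets out to remove, and the scope of 11.5.3 needs stating. This is a worthwhile, inexpensive improvement and not a flaw that invalidates the sub-study.

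**What to change.** In 11.5.2, 11.5.4 and the matching MPP bullet of 6.2, replace the cardiovascular condition with a requirement that every hospital admission, whatever its cause, from MPP enrollment to the final MPP visit be reported with its discharge summary and with the 11.5.3 questions answered. Amend the reference to protocol-defined hospitalizations in 11.3.4 to match. The committee then makes the cardiovascular / non-cardiovascular and heart failure / non-heart-failure calls, still by primary admission diagnosis. This treats admissions as the plan already treats deaths, and it settles the scope of 11.5.3.

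The cost is protocol wording plus a modest number of extra reports and committee reviews: at most 100 subjects × 0.5 years = about 50 subject-years, using the existing committee and classes. Sample size, alpha and power do not change.
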